Minority men experience disparities in prostate cancer knowledge, care patterns, and suffer from more functional outcome morbidity in prostate cancer. Combined, these compound known disease burden differences in these populations. Studies have documented lower levels of knowledge about PCa among African American men compared with other racial groups.²⁴ Historically, AA men are less likely to receive radiation therapy or undergo surgery, and more likely to receive “watchful waiting” or active surveillance, despite having a higher incidence of intermediate and high-risk PCa.²⁵⁻³¹ If rates of definitive therapy for minority patients with high-risk PCa were commensurate with the general population, the burden of the disease could arguably be reduced considerably. Conversely, minority men who do undergo definitive therapy are more likely to experience more treatment regret and greater functional outcome burden.^{32,33} Although little research has been dedicated to treatment variation in Native American men, a recent report suggested that this underserved population also has lower rates of definitive treatment following a diagnosis of PCa.¹⁶ These data suggest a precarious dilemma: on the one hand greater use of aggressive therapies could save lives, but could at the same time exacerbate existing disparities in functional outcomes associated with aggressive therapy.

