1.5 Design and Intervention Plan

Study population: Eligible patients from participating NCORP CCDR components will be enrolled. Men with self-reported racial/ethnic categories American Indian/Alaska Native, African American, Hispanic/Latino as well as all other races using existing 2010 Census definitions will be included. In addition to the Alliance NCORP CCDR sites, this study will be open to non-Alliance NCORP CCDR institutions interested in participating through the CTSU mechanism. Due to geographic clustering of African American and Native American populations, institutions will be selected preferentially if they can recruit at least half of their overall cohort from one of these two patient populations. We anticipate at least 8 sites preferentially accruing half of their participants as African American and another 8 sites who can preferentially recruit half of their participants as Native American. The trial will encourage Hispanic/Latino men to participate at all sites.

Randomization: In order to facilitate decision aid administration, enhance patient compliance, and avoid treatment arm contamination; we will perform a cluster randomized four-arm clinical trial.⁷⁰ We intend to test both during-consultation, pre-consultation and the combination of both during-consultation and pre-consultation evidence-based decision aids using a novel 2x2 factorial design in two key populations. A 2x2 factorial design breaks the combinations of during-consultation and pre-consultation decision aids into four treatment arms (cells): A) Prostate Choice in-visit combined with Knowing Your Options pre-consultation decision aid; B) Prostate Choice within specialty consultations and usual pre-consultation care; C) Usual during-consultation care and Knowing Your Options decision aid prior to the consultation; and D) Usual during-consultation care and Usual pre-consultation care.

In order to answer our question in a manner that preserves strong internal validity, a randomized design is preferred.^{70,71} This approach allows inferences about effects with less concern about baseline imbalances between groups, confounding, or chance. We selected a cluster-randomized design to bring the rigor of the randomized design in line with the reality of every day practice. Furthermore, a cluster-randomized approach avoids contamination effects in the intervention arms.

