4.3 Patient Registration Requirements

- **Informed consent:** the patient must be aware of the neoplastic nature of his/her disease and willingly consent after being informed of the procedure to be followed, the experimental nature of the interventions being tested, alternatives, potential benefits, side-effects, risks, and discomforts. Current human subjects protection committee approval of this protocol and a consent form is required prior to patient consent and registration.
- **Patient completed booklets:** Patient questionnaire booklets are to be ordered prior to the registration of any patients. Patient completed booklets can be ordered by downloading and completing the booklet order form (located under the supplemental documents section of the A191402CD website) and faxing the form to Attn: Operational Support Clerk at [REDACTED]. Samples of the booklets are found in Appendices I and II, which are to be used for reference and IRB submission only. They are not to be used for patient completion.

- **Institutional randomization:** Institutions will be randomized to one of four intervention arms:
 - 1) During- and pre-consultation decision aids
 - 2) Pre-consultation decision aid only
 - 3) During-consultation decision aid only
 - 4) Usual care

The Alliance Statistics and Data Center will randomize institutions once an institution is interested and eligible to participate. All men enrolled at a site will receive the intervention to which the treating institution is randomized.

Specifically, the lead study statistician will randomly assign the initial participating institutions to one of the arms before the study is activated. The randomization will be stratified by center type (i.e. which minority group, if any, the center is “targeting”); so that if for example, there were four initial centers which specialized in Native American/Native Alaskan men, each would be assigned to one of the four arms by randomly selecting one of the four repeatedly without replacement, each time assigning that center to one of the remaining arms. This will be done separately for all center types. For all of these centers, the lead statistician will obtain CTEP Institutional IDs (as well as IDs for affiliates, if any, that may be participating), and will then provide the Alliance randomization center with the initial set of CTEP IDs for each treatment arm.

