4.5 Stratification and Treatment Assignments

While not formal stratification factors, randomization will be set up so that sites will the particular capacities to oversample minority populations will be distributed between the arms, as illustrated in the diagram below.

Grouping Factors/Treatment assignments:

- Arm 1: Pre -and During Consultation Decision Aids
- Arm 2: Pre-Consultation Decision Aid only
- Arm 3: During Consultation Decision Aid only
- Arm 4: Usual Care

5.0**STUDY CALENDAR**

Laboratory and clinical parameters during treatment are to be followed using individual institutional guidelines and the best clinical judgment of the responsible physician. It is expected that patients on this study will be cared for by physicians experienced in the treatment and supportive care of patients on this trial.

Pre-Study Testing Intervals

- To be completed \leq 28 DAYS before registration: History and physical.
- To be completed \leq 90 DAYS before registration: PSA
- To be completed \leq 4 MONTHS before registration: Prostate Biopsy

	Prior to Registration	Baseline*	12 months after baseline**
Test and Observations			
History and Physical	X		
Height	X		
Weight	X		
Prostate biopsy	X		
Chart Review			X(1)
Labs and Staging			
PSA	X		
QOL Instruments			
Baseline Questionnaire		X(2)	
One-year Questionnaire			X(3)

* To be administered following the surgical consultation

** +/- 6 weeks

- 1 At 12 months site staff will review the patient's chart from the 6-month point to the 12-month time-point, collecting treatment information and any pertinent events.
- 2 Includes the Prostate Cancer Treatment Questionnaire and the Decisional Conflict Scale. See Section 10.0 and Appendix I.
- 3 Includes Expanded Prostate Cancer Index Composite (EPIC-26) and the Decisional Regret Scale. See Section 10.0 and Appendix II. To be completed by the patient during a clinic visit. If no clinic visit is scheduled +/- 6 weeks from the 12-month time-point, study staff should mail the 12-month questionnaire with a self-addressed stamped envelope to the patient for him to complete at home and return by mail (see Section 8.3.1).

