12.2.1 Analysis Plan

Although the randomization unit will be participating site, our inferential unit for statistical analysis will be the individual patient. Due to the potential for correlation among patients within the same site, a mixed effects regression model (also known as random effects model or multi-level model) will be utilized to examine the effects of the during-consultation Prostate Choice and the pre-consultation Knowing Your Options decision aids. Specifically, this model will contain a fixed intercept, a fixed effect for having received Prostate Choice, a fixed effect for having received Knowing Your Options, and a random, site-specific intercept to allow patients within the same site to be correlated. Baseline patient-level characteristics including race, ethnicity, severity of disease and site-level characteristics may be incorporated in this model if deemed appropriate. A similar approach will be utilized in the statistical analysis of secondary endpoints. Furthermore, descriptive statistics will be reported after incorporating cluster information, in particular, the empirical cluster size, and the observed intra-cluster correlation.

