12.2.2 Sample Size and Power Considerations

Sample size and power calculation: We first consider power and sample size under the assumption that patients within the same site are uncorrelated. As this is unlikely to be the case in a group randomized trial, we will discuss the adjustment of the sample size estimate to account for this correlation between patients in the next subsection. A recent Cochrane review suggests that most patients can accurately answer 50% (standard deviation of 12%) of the questions asked of them.⁷⁰ On average, DAs increase that knowledge by 20% to 60% of questions asked being answered correctly, but 95% of trials show absolute knowledge increases of 10% or greater. We will consider an absolute 8% increase in knowledge as a clinically meaningful effect size for either during-consultation Prostate Choice or pre-consultation DA in this clinical trial. Note that the four arms of this study make up a 2 X 2 factorial design. Thus, it is natural to consider evaluating the decision aids using a two-way analysis of variance (ANOVA). In this case, the two factors in the ANOVA will be having received during-consultation Prostate Choice (yes or no) and having received pre-consultation DA (yes or no). We will consider simultaneously testing (at a significance level of 0.025 for each test) the main effects of the two decision aids as our primary analysis. That is, we will simultaneously test the null hypothesis that the average knowledge (i.e. the proportion of correct responses to questions) among those who received the pre-consultation DA is equal to that among those who did not (vs. an alternative that these two averages are not equal), and the null hypothesis that the average knowledge among those who received the during-consultation Prostate Choice is equal to that among those who did not (vs. an alternative that these two averages are not equal). A total sample of 100 patients (25 patients per arm) would give us approximately 85% power to detect a difference between those receiving pre-consultation DA and those not receiving pre-consultation DA, under the alternative that the average knowledge among those receiving pre-consultation DA is 58%, and that the average knowledge among those not receiving pre-consultation DA is 50%, using a two-sample t-test (with two-sided alternative) with a 2.5% significance level (this is equivalent to the F test for the main effects in the ANOVA). Under a similar alternative, the same can be said for the during-consultation Prostate Choice decision aid. Thus, if patients within each site were not correlated with each other, our target sample size would be 100 patients. There will be some, but insufficient power to detect an interaction between the two decision aids, but such effects are rare and not anticipated in this study. Therefore, we will not test for such an interaction in the primary analysis.

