
Sample size adjustment due to cluster randomization: As mentioned above, we do not believe that subjects within each site will truly be independent of each other. Thus, the application of the standard sample size calculation, as above, may lead to an underpowered study. Since we expect $k=20$ sites to participate in this clinical trial, we would need about $m = 5$ patients to be enrolled from each site (on average) to achieve a total enrollment of 100 patients. Assuming the intra-site correlation coefficient ρ will be approximately 0.1 (rather than zero) for all study sites, we must inflate the target sample size by a factor⁷¹ of $1+(m-1)\rho=1+(5-1)*0.1=1.4$ to achieve comparable power to that in a patient-level randomized trial. This comes about as follows (we consider the pre-decision DA here, but the same derivation holds for the during-consultation Prostate Choice). Suppose the variance of knowledge (Y) is the same for all patients, and is equal to σ^2 , and that n is our total sample size, with $n/2$ patients receiving the pre-consultation DA and $n/2$ not receiving the pre-consultation DA. Assuming no correlation between patients within the same site, the variance of the sample mean of knowledge among those receiving pre-consultation DA (\bar{Y}_1) will be $\sigma^2/(n/2)$, as will that for the sample mean of knowledge among those not receiving pre-consultation DA (\bar{Y}_2), and our test statistic would have the form $[(\bar{Y}_1 - \bar{Y}_2) - (\mu_1 - \mu_2)]/[\sigma^2/(n/2) + \sigma^2/(n/2)]^{(1/2)}$ (note that the denominator of this statistic simplifies to $[4\sigma^2/n]^{(1/2)}$). However, this is not a correct assumption in our case. In particular, suppose that we have 20 sites, and within each site, we have m (5) patients, between each of whom the

correlation is ρ (0.1) (meaning the covariance between any two patients in the same site is $\rho\sigma^2$). In this case, the variances of the sample means are not $\sigma^2/(n/2)$, but rather:

$$\begin{aligned}
 Var(Y_1) &= Var(Y_2) = Var\left(\frac{1}{\binom{n}{2}} \sum Y_i\right) \\
 &= \frac{1}{\binom{n}{2}^2} \left[\binom{n}{2} \sigma^2 + (2) \binom{\binom{n}{2}}{m} \left(\frac{m!}{(m-2)! 2!} \right) \rho \sigma^2 \right] \\
 &= \frac{1}{\binom{n}{2}} \left[\sigma^2 + \left(\frac{1}{m} \right) m(m-1) \rho \sigma^2 \right] \\
 &= \frac{1}{\binom{n}{2}} [\sigma^2 + (m-1)\rho\sigma^2] \\
 &= \frac{\sigma^2}{\binom{n}{2}} [1 + (m-1)\rho].
 \end{aligned}$$

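### Sites are randomized within center type, but the primary model does not require center type; fixing it in advance, with small-sample degrees of freedom, is a near-free gain

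*Combined protocol and SAP*

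**What the plan says.** On the design, 4.3 (institutional randomization) states: "The randomization will be stratified by center type". Initial sites of each type are dealt to the four arms without replacement, and sites that join later follow a random sequence prepared for their type. Section 4.5 describes the same arrangement differently: "While not formal stratification factors, randomization will be set up so that sites" with the capacity to oversample minority men are spread over the arms.

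On the analysis, 12.2.1 lists an intercept, one fixed effect for each decision aid, and "a random, site-specific intercept to allow patients within the same site to be correlated". Race, ethnicity, disease severity and site characteristics are optional: "site-level characteristics may be incorporated in this model if deemed appropriate". No decision-maker, timing or criterion is given, and no method for degrees of freedom.

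On numbers of sites, 12.2.2 says: "Since we expect $k=20$ sites to participate in this clinical trial". Section 1.5 says: "We anticipate at least 8 sites preferentially accruing half of their participants as African American and another 8 sites" that can do the same for Native American men.

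On whether center type might matter, 1.1 says: "Studies have documented lower levels of knowledge about PCa among African American men compared with other racial groups". It gives no figure, and none of the documents gives a difference in knowledge between center types.

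**The concern.** Balancing arms within center type takes differences between types out of the arm comparison. A model that ignores center type still counts those differences as unexplained site-to-site variation. If they exist, the estimated standard error is larger than the true one, the test is less sensitive than the design allows, and intervals are wider than they need be. With about 20 sites, between-site variation is a large part of the error.

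The second issue does not depend on how large those differences are. Section 12.2.1 leaves four groups of covariates open (race, ethnicity, severity, site characteristics). Counting each group as in or out gives 2 × 2 × 2 × 2 = 16 possible primary models, and nothing prevents the choice from being made with outcome data in hand. Section 12.2.3 also applies repeated interim efficacy looks to this model.

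**Working it through.** **Inputs from 12.2.2.** SD 12 points, target difference 8 points, ICC 0.1, 20 sites, two main-effect tests, each two-sided "at a significance level of 0.025 for each test"; 140 men after cluster adjustment (7 per site) and 172 enrolled (172/20 = 8.6 per site).

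**Assumptions.** From 1.5, 8 African American-oriented and 8 AI/AN-oriented sites; the other 4 as a third type is assumed. Sites are of equal size and exactly balanced, so each arm has 2 + 2 + 1 = 5 sites. Let f be the share of between-site variance explained by center type. The documents do not give f, so it is varied.

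**Plan's own figure.** With 100 independent men, SE = √(4 × 144/100) = 2.40. The noncentral t with 98 df gives 85.3% power, matching the stated figure of about 85%. The cluster step also reproduces: 100 × [1 + (5 − 1) × 0.1] = 140.

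**Standard error with center type in the model.** The residual variance of a site mean is V = 144 × [0.1(1 − f) + 0.9/m]. Each main effect compares 10 sites with 10, so SE = √(V × 4/20). At m = 8.6:
- f = 0: V = 29.47, SE = 2.43
- f = 0.25: V = 25.87, SE = 2.27
- f = 0.50: V = 22.27, SE = 2.11

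**Standard error with center type left out.** The center-type sum of squares, 20 × f × 14.4 (where 14.4 = 0.1 × 144), falls into the 17 residual df, so V becomes V + (20/17) × 14.4f. At f = 0.50 this is 22.27 + 8.47 = 30.74, and the reported SE is √(30.74/5) = 2.48. The true SE is 2.11, so it is overstated by about 17%.

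**Power and type I error.** Site-level simulation, 200,000 replicates per scenario, t reference on 17 df (omitted) or 15 df (included); 172 men, ICC 0.1:

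| f | SE overstated by | Power, omitted | Power, included | Type I error, omitted |
|---|---|---|---|---|
| 0 | 0% | 79% | 78% | 0.025 |
| 0.10 | 3% | 79% | 80% | 0.022 |
| 0.25 | 8% | 80% | 84% | 0.017 |
| 0.50 | 17% | 80% | 89% | 0.010 |

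Type I error with center type included is 0.025 throughout. With 140 men, power omitted v included is 74% v 73%, 74% v 78% and 75% v 84% at f = 0, 0.25 and 0.50. The gain grows with the ICC: at ICC 0.2, 172 men and f = 0.50 it is 61% v 80%.

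**Critical values.** With normal critical values (2.24) in place of t (2.46 on 17 df), type I error at f = 0 is about 0.039 omitted. Included, it is about 0.04 at every f. At f = 0.25 the omitted model gives about 0.027, still above 0.025.

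**The case against.** A reader might infer that the planned error bars are too wide and that the trial loses power against its plan. The documents do not support either statement.

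- **No effect size is given.** Section 1.1 is qualitative and concerns African American men only; it says nothing on knowledge among AI/AN men. At f = 0 nothing is lost.
- **The larger shares need sizeable differences.** Suppose only the 8 African American-oriented sites differ, by d. The variance of center-type means is then 0.4 × 0.6 × d². Setting this to 14.4f gives d = 2.4, 3.9 and 5.5 points at f = 0.10, 0.25 and 0.50. If half the men there are African American (1.5), none elsewhere are, and race is the only cause, the gap between patients is twice that: 4.9, 7.7 and 11.0 points. The second is already close to the 8-point target effect.
- **Planned power never assumed adjustment.** Without center type, power stays at 79% to 80% across these values of f. The gap from there to the stated 85% comes from using 17 site-level df; on patient-level df the same standard error gives about 85%. That is a separate matter.
- **The test need not be conservative.** Section 12.2.1 names no reference distribution, and under normal critical values the omitted model is anti-conservative at small f.
- **Optional race and ethnicity terms** could absorb part of a center-type effect.
- **The difference between 4.3 and 4.5 is one of labeling.** Both spread sites over arms by type.

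All of this stands, and it limits the size and certainty of the claim. It does not give a reason to leave out a factor that the trial already randomizes by, or to leave the primary model undecided.

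**Conclusion.** The point holds as a conditional efficiency gain together with a pre-specification gap. If center type is related to knowledge, omitting it forgoes about 1, 4 and 9 points of power at f = 0.10, 0.25 and 0.50 (172 men, ICC 0.1). If it is unrelated, including it costs about 1 point. The comparison is with an adjusted analysis and not with any power that the plan states.

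The figures rest on the 8/8/4 split, equal site sizes and exact balance within type. Section 4.3 does not say that the sequence for later sites is blocked, so actual balance may be weaker and the figures would change. The openness of the model to data-driven choice does not depend on f. This is an improvement that costs almost nothing; the documents do not show an error that invalidates the primary analysis.

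**What to change.** In 12.2.1, write the primary model as fixed effects for Prostate Choice, Knowing Your Options and center type as used in the randomization, plus the random site intercept. Name a small-sample method (for example Kenward-Roger or between-site degrees of freedom). Adding center type without one would leave type I error near 0.04.

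Replace the clause that leaves covariates to later judgment with this fixed model. Make models that add race/ethnicity and disease severity pre-specified sensitivity analyses, with severity defined. They are not proposed for the primary model because their effect was not examined here and some planned race cells in 12.7 are very small (2, 4 and 5 men).

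Use the same center-type term in the linear secondary models of 12.4.2. Reword 4.5 to agree with 4.3 that center type is a stratification factor.

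The cost is wording and two site-level degrees of freedom (17 to 15). Center type is known when a site is randomized, so no new data are needed.

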12.2.2 Sample Size and Power Considerations

Sample size and power calculation: We first consider power and sample size under the assumption that patients within the same site are uncorrelated. As this is unlikely to be the case in a group randomized trial, we will discuss the adjustment of the sample size estimate to account for this correlation between patients in the next subsection. A recent Cochrane review suggests that most patients can accurately answer 50% (standard deviation of 12%) of the questions asked of them.⁷⁰ On average, DAs increase that knowledge by 20% to 60% of questions asked being answered correctly, but 95% of trials show absolute knowledge increases of 10% or greater. We will consider an absolute 8% increase in knowledge as a clinically meaningful effect size for either during-consultation Prostate Choice or pre-consultation DA in this clinical trial. Note that the four arms of this study make up a 2 X 2 factorial design. Thus, it is natural to consider evaluating the decision aids using a two-way analysis of variance (ANOVA). In this case, the two factors in the ANOVA will be having received during-consultation Prostate Choice (yes or no) and having received pre-consultation DA (yes or no). We will consider simultaneously testing (at a significance level of 0.025 for each test) the main effects of the two decision aids as our primary analysis. That is, we will simultaneously test the null hypothesis that the average knowledge (i.e. the proportion of correct responses to questions) among those who received the pre-consultation DA is equal to that among those who did not (vs. an alternative that these two averages are not equal), and the null hypothesis that the average knowledge among those who received the during-consultation Prostate Choice is equal to that among those who did not (vs. an alternative that these two averages are not equal). A total sample of 100 patients (25 patients per arm) would give us approximately 85% power to detect a difference between those receiving pre-consultation DA and those not receiving pre-consultation DA, under the alternative that the average knowledge among those receiving pre-consultation DA is 58%, and that the average knowledge among those not receiving pre-consultation DA is 50%, using a two-sample t-test (with two-sided alternative) with a 2.5% significance level (this is equivalent to the F test for the main effects in the ANOVA). Under a similar alternative, the same can be said for the during-consultation Prostate Choice decision aid. Thus, if patients within each site were not correlated with each other, our target sample size would be 100 patients. There will be some, but insufficient power to detect an interaction between the two decision aids, but such effects are rare and not anticipated in this study. Therefore, we will not test for such an interaction in the primary analysis.

Sample size adjustment due to cluster randomization: As mentioned above, we do not believe that subjects within each site will truly be independent of each other. Thus, the application of the standard sample size calculation, as above, may lead to an underpowered study. Since we expect $k=20$ sites to participate in this clinical trial, we would need about $m = 5$ patients to be enrolled from each site (on average) to achieve a total enrollment of 100 patients. Assuming the intra-site correlation coefficient ρ will be approximately 0.1 (rather than zero) for all study sites, we must inflate the target sample size by a factor⁷¹ of $1+(m-1)\rho=1+(5-1)*0.1=1.4$ to achieve comparable power to that in a patient-level randomized trial. This comes about as follows (we consider the pre-decision DA here, but the same derivation holds for the during-consultation Prostate Choice). Suppose the variance of knowledge (Y) is the same for all patients, and is equal to σ^2 , and that n is our total sample size, with $n/2$ patients receiving the pre-consultation DA and $n/2$ not receiving the pre-consultation DA. Assuming no correlation between patients within the same site, the variance of the sample mean of knowledge among those receiving pre-consultation DA (\bar{Y}_1) will be $\sigma^2/(n/2)$, as will that for the sample mean of knowledge among those not receiving pre-consultation DA (\bar{Y}_2), and our test statistic would have the form $[(\bar{Y}_1 - \bar{Y}_2) - (\mu_1 - \mu_2)]/[\sigma^2/(n/2) + \sigma^2/(n/2)]^{(1/2)}$ (note that the denominator of this statistic simplifies to $[4\sigma^2/n]^{(1/2)}$). However, this is not a correct assumption in our case. In particular, suppose that we have 20 sites, and within each site, we have m (5) patients, between each of whom the

correlation is ρ (0.1) (meaning the covariance between any two patients in the same site is $\rho\sigma^2$). In this case, the variances of the sample means are not $\sigma^2/(n/2)$, but rather:

$$\begin{aligned}
 Var(Y_1) &= Var(Y_2) = Var\left(\frac{1}{\binom{n}{2}} \sum Y_i\right) \\
 &= \frac{1}{\binom{n}{2}^2} \left[\binom{n}{2} \sigma^2 + (2) \binom{\binom{n}{2}}{m} \left(\frac{m!}{(m-2)! 2!} \right) \rho \sigma^2 \right] \\
 &= \frac{1}{\binom{n}{2}} \left[\sigma^2 + \left(\frac{1}{m} \right) m(m-1) \rho \sigma^2 \right] \\
 &= \frac{1}{\binom{n}{2}} [\sigma^2 + (m-1)\rho\sigma^2] \\
 &= \frac{\sigma^2}{\binom{n}{2}} [1 + (m-1)\rho].
 \end{aligned}$$

Thus, the denominator of our test statistic should actually be $[(4\sigma^2/n)(1 + (m-1)\rho)]^{(1/2)}$. Therefore, if we replace the original sample size ($n=100$) with $n(1 + (m-1)\rho) = 100*1.4 = 140$ in the denominator of our original test statistic, we will have a test statistic which accounts for the correlation of 0.1 between subjects within each of the 20 sites. Hence, we will target an effective sample size of 140 patients (approximately 35 patients per arm, 7 patients per site). The total sample size may be further inflated by 20% to account for ineligible, cancel and loss to follow-up for longer term secondary outcomes and allow increased power to detect racial/ethnic differences. Therefore, a total number of 172 patients will be enrolled into this clinical trial. These 172 patients, recruited from 20 participating sites (about 9 patients per site) will receive the intervention (or control) to which their location is randomized.

Though we have chosen to power this study based on an absolute meaningful difference of 8%, we determined the necessary sample size for a range of meaningful differences. In each case, the target power was approximately 85% (thought it varied slightly, as we only considered sizes which were divisible by 20, given the number of expected sites) with joint main effect two-sided t-tests with two-sided alternatives at the 2.5% significance level. These sample sizes are as follows (not adjusted for ineligibility, cancel and loss to follow-up):

Meaningful Difference	Total sample size without correlation within sites	Total sample size adjusted for correlation within sites
4%	360	504
6%	180	252
8%	100	140
10%	60	84
12%	40	56

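### The two primary tests use a fixed 0.025 each, which is valid; Holm at the same 5% familywise level would add about 5 points of power per aid on the plan's figures, with small costs

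*Combined protocol and SAP*

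**What the plan says.** Section 12.2.2 starts from the factorial layout: "Note that the four arms of this study make up a 2 X 2 factorial design". The primary analysis is two main-effect tests: "We will consider simultaneously testing (at a significance level of 0.025 for each test) the main effects of the two decision aids". The power statement uses the same level, "using a two-sample t-test (with two-sided alternative) with a 2.5% significance level", and so does the table of alternative differences at the end of the section, "with joint main effect two-sided t-tests with two-sided alternatives at the 2.5% significance level". The planning figure is "A total sample of 100 patients (25 patients per arm) would give us approximately 85% power", for one main effect, with the same said to hold for the other aid.

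The effect and spread behind that figure are "We will consider an absolute 8% increase in knowledge as a clinically meaningful effect size" and "most patients can accurately answer 50% (standard deviation of 12%) of the questions asked of them". On interaction: "Therefore, we will not test for such an interaction in the primary analysis".

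No step-down or alpha-recycling rule appears. A familywise level is not stated; 5% is implied by 2 × 0.025. Section 12.2.3 adds 5 to 6 interim looks before the final analysis with O'Brien-Fleming boundaries, but gives neither their overall level nor how the two tests share it.

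**The concern.** Testing two hypotheses at a fixed 0.025 each is a Bonferroni split. Once one aid has been declared effective, only one hypothesis can still be falsely rejected, and it can be tested at 0.05 without taking the familywise error above 5%. The fixed split leaves that alpha unused.

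The loss is confined to cases where one aid is significant at 0.025 and the other has a p-value between 0.025 and 0.05. Such cases matter most when both aids work. That scenario is relevant here, because section 1.2 aims to compare the aids alone and in combination. The plan reports power per aid only, so a reader does not see how likely it is that one of two effective aids is missed. Sites and minority accrual are limited, so power that needs no extra men is worth having.

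**Working it through.** **Inputs (12.2.2).** Difference 8 points, SD 12, N = 100 (50 against 50 for each main effect), two-sided 0.025, no interaction, equal arms. Under balance the two main-effect estimates are uncorrelated.

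**1. Reproduce the plan's figure.** The standard error is 12 × √(4/100) = 2.4, and the noncentrality is 8/2.4 = 3.33. With a noncentral t on 98 df, power is 0.853 at 0.025, which agrees with the plan's 85%. At 0.05 it is 0.910.

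**2. Fixed split against Holm.** Write a for power at 0.025 and b for power at 0.05.

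- Both aids, fixed split: a² = 0.853² = 0.727.
- Both aids, Holm: both p-values must be below 0.05 and at least one below 0.025, so b² − (b − a)² = 0.910² − 0.057² = 0.825.
- One given aid, Holm: a + (b − a) × a = 0.853 + 0.057 × 0.853 = 0.902.
- At least one aid, either rule: 1 − (1 − a)² = 0.978.

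A simulation of 1,000,000 runs with a shared residual variance gave 73.0% and 82.5% for both aids, 85.4% and 90.1% per aid, and 97.7% for at least one.

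**3. Error rates under Holm (simulated).** The familywise error is 4.9% with neither aid effective. With one aid null and the other at 8 points, the null aid is rejected in 4.7% of runs. With the other effect very large, this is 5.0%. Under the fixed split the null aid is rejected in about 2.5% in every case.

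**4. Allowing for sites.** With 172 men in 20 sites, m = 8.6. The design effect is 1 + 7.6 × 0.1 = 1.76, and the effective N is 172/1.76 = 97.7. The plan names no degrees-of-freedom method. I assume 17: 20 sites less the intercept and two aid effects. By simulation, power per aid goes from 79% to 85% and both aids from 64% to 76%. If the site-level df are ignored, both aids goes from 72–73% to 82%.

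**5. Dependence on the effect** (N = 100, 98 df, formulas of step 2):

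| True effect, both aids | a | b | Both, fixed | Both, Holm | Gain |
|---|---|---|---|---|---|
| 6 points | 0.590 | 0.697 | 34.8% | 47.4% | 12.6 |
| 8 points | 0.853 | 0.910 | 72.7% | 82.5% | 9.7 |
| 10 points | 0.969 | 0.985 | 94.0% | 97.0% | 3.0 |

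**6. Interim looks.** With O'Brien-Fleming boundaries at 0.025 and 0.05, 6 or 7 looks in total, and both hypotheses followed to the end, the chance of showing both aids goes from 73% to 82%. If the whole trial stopped at the first crossing of either aid, it would be about 16–19% (fixed) against 32–35% (Holm).

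**The case against.** The strongest reply is that nothing here is wrong. The fixed split controls the familywise error, is used consistently, and delivers the per-test power the plan asks for. This stands in full. A reader might infer that the plan mishandles multiplicity or is underpowered by its own standard because of the split; the documents support neither.

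Secondly, showing both aids is not the plan's success criterion. Section 12.2.2 states two separate hypotheses and powers each. This also stands, so the gain of about 5 points per aid is the figure closest to the plan's own measure. The both-aids figure is supplementary. It would also go too far to say the plan forecasts 8 points for both aids: 8 points is the clinically meaningful difference used as the test alternative. The same section cites larger gains from earlier trials, and the futility rule in 12.2.3 uses a target of 0.1. At 10 points the advantage is small.

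Thirdly, a reader might take 73% and 82% as the trial's actual prospects, or regard the change as free. Those figures assume uncorrelated patients and one look, and 12.2.2 itself calls independence unlikely. Nor is the change free: an ineffective aid's own error rate rises when the other aid works, and intervals matching Holm are less simple than two 97.5% intervals. What survives is that Holm never rejects less than the fixed split and needs no more patients.

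**Conclusion.** A cheap improvement to a valid plan. At the same 5% familywise level, Holm raises power per aid from 85% to 90% on the plan's inputs, and from 79% to 85% when 172 men in 20 sites are analysed with site-level degrees of freedom. The gain in showing both aids is about 10 and 12 points respectively.

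These results rest on a true effect of 8 points for both aids, SD 12, no interaction and balanced arms. The second set also rests on an intra-site correlation of 0.1 and the assumed 17 df. With interim looks, a comparable gain holds only if the remaining hypothesis is followed after the first crossing. I would recommend the change but would not hold up the trial for it.

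**What to change.** In 12.2.2, replace the fixed level with: *Holm procedure, familywise two-sided 5%: the smaller p-value is tested at 0.025; if significant, the other is tested at 0.05.* Align the sentence above the sample-size table. The sample sizes can stay: they remain correct for a first test at 0.025 and are conservative for power per aid.

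In 12.2.3, pre-specify O'Brien-Fleming boundaries for each aid at both 0.025 and 0.05. State that an aid moves to its 0.05 boundary once the other has crossed, and that follow-up of the remaining hypothesis then continues. Settle this before any unblinded look.

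The cost is a sentence in 12.2.2, a short addition to 12.2.3, and no extra patients. Acknowledge in the text that the error rate for one ineffective aid can approach 5% when the other works. Report ordinary 95% or 97.5% confidence intervals beside the tests, noting that they do not correspond exactly to the Holm decisions.
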